1.3 Schedule of Activities (SoA)

Study Flow Chart for Individual Patients

Estimated Timeline for Weeks 1-2 (Mapping and Treatment Week)

Monday:

7:30 AM-9:30 AM: 1st Angiographic study for mapping and MAA delivery

10:00 AM-11:00 AM: MAA SPECT/CT (Patient will go to nuclear medicine with radial/femoral arterial access sheath in place)

11:30 AM-1:00 PM: 2nd Angiographic study for low-dose Y90 delivery (After the procedure, patient's femoral sheath will be removed and hemostasis will be achieved with manual compression or closure device. If procedure performed via radial access, which is more commonly performed currently at Emory, the radial sheath will stay in and removed according to IR protocol after Y90 SPECT/CT.)

2:00 PM-3:00 PM: Y90 Bremsstrahlung SPECT/CT

3:00 PM-3:30 PM: Removal of the radial sheath at IR post procedural area and discharge.

4:30-5:30 PM: Y90 PET/CT.

Patient is free to go home after this.

Thursday:

11:00 AM-12:30 PM: 3rd angiographic study to deliver therapeutic dose of Y90.

1:00 PM-2:00 PM: Y90 Bremsstrahlung SPECT/CT (After the procedure, patient's femoral sheath will be removed and hemostasis will be achieved with manual compression or closure device. If procedure performed via radial access, which is more commonly performed currently at Emory, the radial sheath will stay in and removed according to IR protocol after Y90 SPECT/CT.)

3:00 PM-3:30 PM: Removal of the radial sheath at IR post procedural area and discharge.

4:30-5:30 PM: Y90 PET/CT.

Patient is free to go home after this.

Study Procedures	Screening Visit Week 0	Therapy planning/mapping Week 1-2	Y90 sirsphere treatment Week 1-2	1 week post procedure Week 6	1 month post procedure Week 6	3 months post-procedure Week 14	6 months post-procedure Week 26
Informed consent	X						
Entry Criteria	X						
Demographics	X						
Medical/surgical Hx	X						
Blood sampling	X				X	X	X
Collect list of medications	X						
Vital signs	X						
Physical exam	X						
Phone follow-up by [name] or Research Nurse				X			
MRI W & WO contrast	X				X	X	X
Conventional MAA angiography		X					
Low dose Y90 shunt study angiography		X					
SPECT/CT		X	X				
PET/CT		X	X				
Y90 Treatment			X				
Post Procedure Clinic follow up					X	X	X

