4.4 End of Study Definition

A participant is considered to have completed the study if he or she has completed all phases of the study including the last visit or the last scheduled procedure shown in the Schedule of Activities (SoA), Section 1.3.

The end of the study is defined as completion of the last visit or procedure shown in the SoA in the trial globally.

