7.5 Duration of Follow Up

Patients will be followed for approximately 180 days after Y90 therapy according to the SoA's detailed above to determine both safety and efficacy. The patients will then be followed every 3 months as per standard of care at Emory IR. This will generally continue until patient's death, enrollment in hospice or loss to follow-up.

Long-term follow-up should continue until the patient's withdrawal of consent or loss to follow up, death, or study termination. In case of a clinically significant AE, patient will be followed for safety until resolution or permanent sequelae of all toxicities attributable to study drug(s). If the patient discontinues study drug for a clinically significant AE, the patient will be followed until resolution of the AE or the event is considered to be stable and/or chronic.

A participant will be considered lost to follow-up if he fails to return for three scheduled visits and is unable to be contacted by the study site staff after three attempts at contact by phone.

The following actions must be taken if a participant fails to return to the clinic for a required study visit:

- The site will attempt to contact the participant and reschedule the missed visit and counsel the participant on the importance of maintaining the assigned visit schedule and ascertain if the participant wishes to and/or should continue in the study.
- Before a participant is deemed lost to follow-up, the investigator or designee will make every effort to regain contact with the participant (where possible, 3 telephone calls and, if necessary, a certified letter to the participant's last known mailing address or local equivalent methods). These contact attempts should be documented in the participant's medical record or study file.
- Should the participant continue to be unreachable, he will be considered to have withdrawn from the study with a primary reason of lost to follow-up.

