8. STUDY ASSESSMENTS AND PROCEDURES

All patients will undergo baseline liver mass protocol abdominal MRI without and with contrast within 30 days prior to the shunt study, and 1, 3, 6, and 12 months after Y90 RE therapy.

Objective TR will be evaluated longitudinally using mRECIST criteria by [name] with a help of an abdominal radiologist. TDR will be calculated using two different methods: 1. Mean dose of the entire tumor resulting in objective TR; 2. Determination of % tumor volume receiving >100 Gy resulting in objective TR. The reason for the second TDR calculation is to take into account the non-homogeneity of Y90 dose delivered to the tumors previously reported.[27, 28] TDR threshold based on logistic regression will be determined by Drs. [name] and [name].

Additional scan assessments may be collected based on clinical symptoms, as appropriate. Documented tumor measurements are required using CT scans, MRI, physical examination, and/or digital photography, as appropriate. Any imaging used to assess disease at any time point will be submitted for an independent radiology review. The same method of assessment (CT or MRI and/or digital photography) and the same technique for acquisition of images must be used for all

study assessments (contrast must be used unless medically contraindicated). Baseline imaging should be done at the same institution/facility which will be used to measure response during the patient's participation in the study. Radiographic assessments and efficacy analyses will be conducted by the Investigator site as well as the independent radiology review committee.

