9. MEASUREMENT OF EFFECT

Response and progression will be evaluated in this study using m-RECIST [42].

9.1 m-RECIST Criteria

At baseline, tumor lesions/lymph nodes will be categorized as measurable or non-measurable as described in the following subsections.

For the purposes of this study, patients should be re-evaluated for response at 1, 3 and 6 months post Y90 therapy.

Definitions

Evaluable for toxicity. All patients will be evaluable for toxicity from the time of their first treatment with *Y90 therapy*.

Evaluable for objective response. Only those patients who have measurable disease present at baseline, have received Y90 therapy, and have had their disease re-evaluated will be considered evaluable for response. These patients will have their response classified according to the definitions stated below. (Note: Patients who exhibit objective disease progression prior to the completion of study could be considered for alternate therapy after documentation of PD at 3 months.)

Disease Parameters

Measurable disease. Measurable lesions are defined as those that can be accurately measured in at least one dimension (longest diameter to be recorded) as ≥ 20 mm by chest x-ray or as ≥ 10 mm with CT scan, MRI, or calipers by clinical exam. All tumor measurements must be recorded in millimeters (or decimal fractions of centimeters).

Note: Tumor lesions that are situated in a previously irradiated area might or might not be considered measurable. *If the investigator thinks it appropriate to include them, the conditions under which such lesions should be considered must be defined in the protocol.*

Malignant lymph nodes. To be considered pathologically enlarged and measurable, a lymph node must be ≥ 15 mm in short axis when assessed by CT scan (CT scan slice thickness recommended to be no greater than 5 mm). At baseline and in follow-up, only the short axis will be measured and followed.

Non-measurable disease. All other lesions (or sites of disease), including small lesions (longest diameter <10 mm or pathological lymph nodes with ≥ 10 to <15 mm short axis), are considered non-measurable disease. Bone lesions, leptomeningeal disease, ascites, pleural/pericardial effusions, lymphangitis cutis/pulmonitis, inflammatory breast disease, and abdominal masses (not followed by CT or MRI), are considered as non-measurable.

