10.5.4 Analysis of secondary endpoints

Secondary clinical endpoints will be evaluated to assess outcomes including biology of resistance and survival. The endpoints with their definitions are listed as follows:

1. Tumor Dose Response Threshold (TDRT): defined as the Y90 dose that results in CR or PR
2. Tumors with LD 50 and LD 70: Defined at frequency of tumors in which 50% or more or 70% or more of their volume received above TDRT and their correlation with response.
3. Time to progression (TTP): defined as the time from start of protocol therapy until the criteria for disease progression are met. Patients who are either lost to follow-up, die or who begin alternative treatments prior to progression, will have their data censored as of the date considered to be lost to follow-up, date of death, or the first day of alternative therapy.
4. Progression-free survival (PFS): defined as the time from start of protocol therapy to disease progression or death from any cause, censoring patients without an event at time of last clinical assessment.
5. Overall survival (OS): defined as the time from start of protocol therapy to death, censoring patients who are alive at last follow-up

Protocol therapy related toxicities rate will be summarized using descriptive statistics such as frequencies and proportions. Differences in the proportion of patients who experience protocol-related toxicities will not be compared between cohorts.

To compare TDRT and Tumors with LD 50 and LD 70 between two groups, two sample paired t-tests will be conducted when data followed a normal distribution, otherwise Wilcoxon signed rank test will be used instead. General linear model (GLM) will be further used in the multivariable analysis to estimate the adjusted efficacy of treatment (MAA vs Y90) on TDRT and Tumors with LD 50 and LD 70 after adjusting for other factors, respectively. Pearson correlation coefficients will be calculated to measure the correlation between two numerical variables, and the significance of coefficients will be tested using Wald's test.

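### Time to progression is censored when a patient is declared lost, not at the last scan, so unimaged time counts as progression-free

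*Combined protocol and SAP*

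**What the plan says.** Section 10.5.4, item 3, defines TTP from the start of protocol therapy to progression. Patients who are lost, die or begin alternative treatment first "will have their data censored as of the date considered to be lost to follow-up, date of death, or the first day of alternative therapy".

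Section 7.5 describes loss in two ways. The definition reads "A participant will be considered lost to follow-up if he fails to return for three scheduled visits and is unable to be contacted", with three telephone attempts. The bullets that follow start from a single missed required visit, ask staff to try to regain contact, and end by saying that if the patient stays unreachable "he will be considered to have withdrawn from the study with a primary reason of lost to follow-up". No number of missed visits is attached to that last step.

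The imaging schedule also varies between sections:
- Section 9.1: "patients should be re-evaluated for response at 1, 3 and 6 months post Y90 therapy".
- Section 1.3: the row "Post Procedure Clinic follow up" is marked at 1, 3 and 6 months only. The 1-week contact is by telephone.
- Section 4.4: "The end of the study is defined as completion of the last visit or procedure shown in the SoA in the trial globally".
- Section 8 (repeated in 10.4): MRI "within 30 days prior to the shunt study, and 1, 3, 6, and 12 months after Y90 RE therapy". Section 8 also allows extra scans prompted by symptoms.
- Section 7.5, after about 180 days: "The patients will then be followed every 3 months as per standard of care at Emory IR".

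For PFS, the definition within Section 9.1.2 censors lost patients at their last evaluable tumor assessment. Section 10.5.4, item 4, instead uses the last clinical assessment. Neither rule is stated to apply to TTP.

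**The concern.** Progression under m-RECIST is read from images. Once a patient stops being imaged, progression can no longer be recorded, so the last scan is the latest time at which the patient is known to be progression-free. Censoring at a later declaration date keeps the patient in the risk set at assessments where an event could not have been observed. Each such patient adds to the denominator and cannot add to the numerator, which pushes the Kaplan-Meier curve up.

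Section 10.5.4 plans Kaplan-Meier estimates of TTP with attention to early time points and the median, as well as Cox models, so the bias would enter reported figures. If patients whose disease is progressing are more likely to stop attending, the true error is larger than a calculation based on unrelated loss would show.

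**Working it through.** The plan states no TTP sample size, event count or loss rate, so there is no figure of its own to reproduce. The check has three steps.

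**1. Gap between last scan and declaration.** Inputs are the three-missed-visit definition (7.5), scheduled visits at 1, 3 and 6 months (1.3, 9.1) and, as an alternative, 3-monthly visits after that (7.5). Gap = time of the visit that triggers the declaration, minus time of the last scan. Therapy is time 0, and baseline imaging is treated as time 0 although it is earlier.

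| Last scan | Three missed, Schedule of Activities only | Three missed, standard-of-care visits counted | One missed visit (7.5 bullets) |
|---|---|---|---|
| Baseline | month 6, gap 6 − 0 = 6 | month 6, gap 6 | month 1, gap 1 − 0 = 1 |
| Month 1 | cannot be met | month 9, gap 9 − 1 = 8 | month 3, gap 3 − 1 = 2 |
| Month 3 | cannot be met | month 12, gap 12 − 3 = 9 | month 6, gap 6 − 3 = 3 |

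The time taken by the contact attempts comes on top. The 6-month figure agrees with the Schedule of Activities (Week 26 minus Week 1-2 = 24 to 25 weeks). Where the table says the rule cannot be met, the patient has at most two scheduled visits left to miss, and item 3 then supplies no loss date at all.

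**2. Effect on the 6-month estimate, three-missed-visit definition.** Let *p* be the share of treated patients who never return and *S* the true progression-free proportion at 6 months, with loss unrelated to progression. Never-returning patients stay in the risk set through the month-6 assessment without events, so

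reported value = 1 − (1 − *p*)(1 − *S*).

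- *S* = 0.50, *p* = 0.10: 1 − 0.90 × 0.50 = 0.55
- *S* = 0.50, *p* = 0.20: 1 − 0.80 × 0.50 = 0.60
- *S* = 0.30, *p* = 0.10: 1 − 0.90 × 0.70 = 0.37
- *S* = 0.30, *p* = 0.20: 1 − 0.80 × 0.70 = 0.44

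With n = 30, *p* = 0.10 and 0.20 mean 3 and 6 patients. All values of *p* and *S* are assumptions.

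**The same under the one-missed-visit reading.** The never-returning patient is in the risk set at month 1 only. Take exponential TTP with median 6 months (assumed): *S*(1) = 2^(−1/6) = 0.891 and *S*(6) = 0.50. For *p* = 0.10 the month-1 estimate is 1 − 0.90 × 0.109 = 0.902, and the month-6 estimate is 0.902 × 0.50/0.891 = 0.506. For *p* = 0.20 they are 0.913 and 0.512. The direction is the same, but the size is about 1 point instead of 5 to 10.

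**3. A mixed pattern of loss.** A simulation compared the two censoring dates with 200,000 patients per scenario. It assumed exponential TTP with median 6 to 12 months; 10% to 30% loss unrelated to progression; last scan equally likely at baseline, 1, 3 or 6 months; and declaration at the third missed visit, counting 3-monthly visits. Censoring at declaration exceeded censoring at the last scan by 1.6 to 8.2 points at 6 months and 2.7 to 11.6 points at 12 months.

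**The case against.** The strongest reply is that Section 7.5 does not settle when a patient is lost. Its closing bullets can be read as permitting the declaration after one missed visit and failed contact, and then the unimaged credit for a patient who never returns is weeks, not six months. This stands as a limit on size. It does not remove the fault, because the date still falls after the last scan, and two readings of one censoring date are themselves a reason to fix the text.

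A reader might infer that every lost patient is credited with six or more months because the trial has only three visits. The documents do not support that. Counting only those three visits, the definition is reached solely by patients with no post-therapy scan. The 8- and 9-month gaps need the standard-of-care visits to count as scheduled visits.

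A reader might also infer that progression can be seen only on the 1, 3 and 6 month scans. Section 8 allows symptom-driven imaging, and Sections 8 and 10.4 mention a 12-month MRI. These may catch progression in patients still in contact, but not in those who have left.

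TTP is also a minor endpoint here. It is absent from the synopsis endpoints and the Section 3 table, and has no hypothesis or power statement. That is correct and limits the consequence. The provisions on replacing patients (7.6, 7.7, 10.2) do not say that a lost patient leaves the TTP analysis.

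**Conclusion.** The point holds for loss to follow-up. As written, item 3 credits lost patients with progression-free time after their last image and so biases the Kaplan-Meier TTP estimates upward. Under the stated definition, a patient who never returns is credited with about 6 months. The effect on the curve depends on a loss rate that the documents do not give. If 10% never return, a true 50% at 6 months reads as 55%; under the one-missed-visit reading it reads as about 51%. Larger shifts, such as 30% reading as 44%, need 6 of 30 treated patients to attend no follow-up visit at all and are a severe case. All these figures assume loss unrelated to progression.

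It would be tempting to extend the criticism to the death and alternative-therapy dates in the same sentence. The calculations here concern loss only and do not support changing those dates. Nor does the point reach the primary comparison or the n = 30 justification.

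**What to change.** In Section 10.5.4, item 3, censor TTP for patients lost to follow-up at their last evaluable tumor assessment, in line with the PFS definition in Section 9.1.2. A lost patient with no post-therapy scan would then contribute no progression-free time. Use the Section 7.5 date for disposition only, and reconcile the two descriptions of loss in that section, stating which visits count as scheduled.

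The cost is one sentence in the analysis section and a clarification in 7.5, best made before analysis. No new visits or data are needed, since scan dates are already collected. Reported TTP will be somewhat less favourable. The change does not cure bias from sicker patients leaving early, so the number lost and the time of each last scan should be reported beside the curve.

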10.4 Analysis of Secondary Endpoints

1. To Identify tumor dose response thresholds (TDRT) and tumor dose distribution in patients with HCC treated with Y90 resin microspheres.

All patients will undergo baseline liver mass protocol abdominal MRI without and with contrast within 30 days prior to the shunt study, and 1, 3, 6, and 12 months after Y90 RE therapy.

Objective TR will be evaluated longitudinally using mRECIST criteria by [name] with a help of an abdominal radiologist. TDR will be calculated using two different methods: 1. Mean dose of the entire tumor resulting in objective TR; 2. Determination of % tumor volume receiving >100 Gy resulting in objective TR. The reason for the second TDR calculation is to take into account the non-homogeneity of Y90 dose delivered to the tumors previously reported.[27, 28] TDR threshold based on logistic regression will be determined by Drs. [name], [name], and [name].

2. To optimize low dose Y90 techniques in predicting TNR and LSF.

No statistical consideration was deemed necessary for this secondary endpoint.

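### Section 10.5.4 plans paired tests and a GLM of MAA versus Y90 on TDRT and LD 50/LD 70, but these endpoints have no two groups and no pairs to analyse

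*Combined protocol and SAP*

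**What the plan says.** All references are to the combined protocol and SAP.

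- **TDRT.** Section 10.5.4 lists "Tumor Dose Response Threshold (TDRT): defined as the Y90 dose that results in CR or PR". Sections 8 and 10.4 say how it is obtained: "TDR threshold based on logistic regression will be determined". Section 10.4 names two dose metrics. The first is given as "TDR will be calculated using two different methods: 1. Mean dose of the entire tumor resulting in objective TR"; the second is the share of tumor volume above 100 Gy.
- **LD 50 and LD 70.** Section 10.5.4: "Defined at frequency of tumors in which 50% or more or 70% or more of their volume received above TDRT".
- **Planned comparison.** Section 10.5.4: "To compare TDRT and Tumors with LD 50 and LD 70 between two groups, two sample paired t-tests will be conducted". If the data are not normal, "otherwise Wilcoxon signed rank test will be used instead". A general linear model (GLM) is then to "estimate the adjusted efficacy of treatment (MAA vs Y90) on TDRT and Tumors with LD 50 and LD 70", adjusting for other factors.
- **Design.** The trial is single arm, and every patient has both mapping studies (Section 4.1). Therapeutic activity is planned from MAA SPECT alone (Sections 7.1.2 and 8.1, item G). Delivered dose and dose-volume histograms (DVHs) come from the post-therapy PET/CT (Section 8.1, item K). Up to three lesions per patient are eligible (Section 5.1, criterion e).

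The statistical sections define no MAA version and no Y90 version of TDRT, LD 50 or LD 70. They also give no rule for several tumors in one patient.

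**The concern.** A paired test needs two measurements of the same quantity on each of many units. TDRT is a parameter estimated once from the whole cohort, not something measured on a patient. LD 50 and LD 70 classify a tumor by the dose it actually received, and it received that dose under one plan. The MAA-versus-Y90 contrast, which makes sense for lung shunt fraction and tumor-to-normal ratio, has been carried over to endpoints where it has no counterpart.

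TDRT is a named secondary objective (Synopsis and Section 3). An analyst told to carry out this paragraph would have to invent the unit, the pairing and the groups after seeing the data. One likely improvisation is to take the doses of responding tumors as per-patient TDRT values. That selects on the outcome and does not estimate a threshold.

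**Working it through.** **No figure to reproduce.** The plan states no sample size, power or alpha for these tests; Section 10.2 covers LSF and TNR only. The check is of the endpoint definitions, followed by what each planned test can return.

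**1. TDRT: what can be paired.** A logistic regression of response on dose gives one threshold per fitted model. With two dose metrics there are two thresholds, both from delivered dose. That gives no MAA/Y90 pairs. The second treatment that Section 7.4.1 allows in some cases would not create a tracer pair either.

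Suppose, generously, that a threshold is refitted on each tracer's predicted dose. Then n = 1 pair per metric.

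- Paired t-test: df = n − 1 = 1 − 1 = 0. The SD of the difference, the statistic and the p-value are undefined.
- Signed rank: smallest two-sided p = 2 × (1/2)^n = 2 × 0.5 = 1.0.
- Pooling both metrics, although one is in Gy and the other in percent of volume: n = 2, smallest p = 2 × 0.25 = 0.50.
- GLM: two observations less two parameters (intercept and tracer) leaves 0 residual df, before any adjustment factor is added.

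So the fallback does not help TDRT, and neither does the GLM.

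**2. LD 50/LD 70 as defined.** The criterion is volume that received dose above TDRT. Each tumor has one delivered dose map, so it has one yes/no value and no pair. A linear model is also a poor choice for a yes/no outcome.

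**3. LD 50/LD 70 if pairs were built from predicted-dose maps.** Differences can only be −1, 0 or 1. They are never normal, so the plan's own condition leads to the signed-rank test. All non-zero differences share one rank, so with zeros dropped the statistic reduces to (b − c)/√(b + c), the uncorrected McNemar statistic, where b and c are the discordant counts. Illustration with b = 8, c = 2 among 30 tumors:

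- Signed rank and McNemar: z = 6/√10 = 1.90, p = 0.058.
- Paired t: p = 0.056.
- Exact McNemar: p = 0.109.

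A yes/no outcome therefore does not by itself make the result invalid.

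**4. Several tumors per patient.** Simulated type I error at nominal 5%, treating tumors as independent. The assumptions are not from the documents: 30 patients, latent within-pair correlation 0.5, marginal rate 0.5 to 0.95, tracer-specific variance 0, 50 or 90% at patient level, 3,000 runs per setting. The paired t-test and the signed-rank test gave the same rates.

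| Tumors per patient | No patient-level clustering | 50–90% at patient level |
|---|---|---|
| 1 | 1.6–5.2% | not applicable |
| 2 | 4.3–5.3% | 6.3–11.0% |
| 3 | 4.4–5.5% | 7.8–16.1% |

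Even if pairs were constructed, ignoring the clustering could roughly double or triple the error rate.

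**The case against.** The strongest defence is that the wording allows a per-tumor reading. Both the definition in Section 10.5.4 and the first metric in Section 10.4 could mean the dose in each responding tumor. Section 4.1 compares the delivered dose with the dose predicted by MAA and by low-dose Y90, so paired predicted doses will exist. That last part stands, and the fix uses it. It does not rescue the planned test. On that reading the delivered dose is still one value per tumor, and comparing predicted doses among responders leaves out the non-responders, without whom there is no threshold.

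A second defence is that the signed-rank fallback handles the yes/no endpoints. This also stands in part. With constructed pairs and one tumor per patient it is in effect McNemar's test and does not inflate the error rate (about 2–5% in the simulation). A reader might infer that LD 50/LD 70 cannot be tested merely because they are yes/no; step 3 shows that this goes too far. The firmer defects are the missing pair, the undefined groups and the unhandled lesions.

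Third, these are secondary analyses without a power claim. That is correct and limits the severity.

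**Conclusion.** The comparison of TDRT and LD 50/LD 70 between MAA and Y90 cannot be carried out as written. For TDRT there are no pairs under the plan's definitions, and at most one per dose metric under a generous reading, which gives 0 degrees of freedom and a signed-rank p-value of 1.0. For LD 50/LD 70 there is one value per tumor, with clustering of up to three lesions ignored. This rests on the definitions in Sections 8, 10.4 and 10.5.4 and on therapy being planned from MAA alone. Only the type I error figures rest on outside assumptions.

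Three stronger readings are not supported:

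- A reader might infer that no other planned tracer comparison bears on tumor outcome. Section 10.5.4 also plans Cox models of MAA versus Y90 on time to progression, PFS and OS, although these too lack two treatment groups.
- A reader might try to count the tumors on which the tracers disagree. The documents give no discordance rate, and 30 patients with one to three lesions means 30 to 90 tumors.
- A reader might infer that the primary results are compromised. LSF and TNR are measured per patient with each tracer, and the logistic-regression estimate of TDRT itself is not affected by this defect.

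The change should be made. It concerns a secondary endpoint, the defect is clear and the repair is cheap.

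**What to change.** Rewrite the comparison paragraph of Section 10.5.4:

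1. Delete the paired t-test, the signed-rank test and the GLM for TDRT and LD 50/LD 70.
2. Report TDRT from delivered dose, separately for each dose metric, with a 95% confidence interval from a bootstrap that resamples patients. State the response probability that defines the threshold and the visit at which response is read.
3. Report LD 50 and LD 70 as proportions of tumors. Relate them to response with a logistic/GEE model clustered by patient. Because TDRT is estimated from the same responses, re-estimate it within each resample or label the association descriptive.
4. If a tracer comparison is wanted, compare MAA-predicted and low-dose-Y90-predicted mean tumor dose from the partition model, each against the delivered dose, as paired errors clustered by patient. Label it exploratory.
5. Keep any tracer comparison of percent volume above 100 Gy or of LD status (McNemar with one tumor per patient, otherwise clustered logistic/GEE) optional.

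**Cost.** Items 1 to 4 need a rewritten paragraph and a little more analysis work, using doses already planned. Item 5 is not free. Section 8.1, item K plans DVHs only from the post-therapy PET/CT, and the partition model assumes uniform uptake within the tumor (Section 2.1), so DVH work on the pre-treatment scans would be additional. Section 2.2.2 also reports very few counts on low-dose PET in the phantom. All intervals will be wide with 30 patients.
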